Connect2BWell: An Evidence-Based Screening, Brief Intervention, and Referral to Treatment
(SBIRT) Program

NCT04745065

Unique Protocol ID: R44DA0448400

09/16/2021

This clinical trial evaluated *Connect2BWell*, a theoretically-grounded, mobile-optimized substance use risk intervention. *Connect2BWell* is a computer-tailored intervention (CTI) for adult primary care patients who misuse alcohol or other drugs. This program is tailored to each patient in the following ways:

1. Their most problematic drug (i.e., the drug with the highest risk score)
2. Their risk severity (i.e., moderate or high) for their most problematic drug
3. Their readiness to quit their most problematic drug or, for prescription drugs, to use as prescribed
4. Their readiness to seek treatment if their risk severity score is in the “high” range

The *Connect2BWell* program has many different components including:

1. A CTI that delivers three online sessions with assessments, feedback, and guidance matched to each patient on the dimensions above
2. Three one-on-one SBIRT brief intervention sessions delivered in person or via telehealth by a healthcare provider trained in SBIRT and the *Connect2BWell* program
3. Clinical Dashboard that presents the patients’ results and responses from the CTI, to guide “change talk” and the collaborative selection of action steps during the one-on-one intervention sessions
4. Patient Portal that allows the patient to view and track their action steps, and that presents online information and activities designed to increase key skills for reducing substance use (e.g., dealing with cravings) and increase well-being
5. Daily text messages with stage and drug-matched messages to patients, to facilitate change and increase well-being
6. PDFs with SBIRT screening and intervention session results that are sent to the patient’s electronic health record (EHR)

ProChange collaborated with our partner the Community Health Center (CHC), the leading independent, non-profit healthcare provider in the state of Connecticut, providing comprehensive primary care services in medicine, dentistry, and behavioral health to more than 145,000 people. Two approaches were used to recruit patients to participate in the clinical trial: a “Universal Approach” and a “Targeted Approach,” as described below.

Universal Approach: At the same time each day, the CHC Business Intelligence Department (BI) ran an automated query on CHC’s electronic data warehouse to identify patients who meet specified criteria. This list of patients and corresponding information was transmitted to a Pro-Change system that automatically sent each patient an email invitation in their preferred language. Patients who did not click on the link to start the study receive additional invitations at 1, 2, and 3 days’ follow-up, with a telephone call on day 4 from the CHC Project Manager to a random sample of non-respondents. After clicking on the email link and registering, patients saw a description of the study that presented many elements of informed consent and had the option to: 1) decline participation, 2) continue to the online screener, or 3) simply close out of the program. Patients who begin the online screener but did not complete it received up to five automatic reminders via email at 1, 2, 3, 5, and 6 days to return to their session to complete it.

Targeted Approach. This approach targeted individuals who hadn't completed the Connect2BWell-administered ASSIST measure before their scheduled medical appointment, and instead complete—and screened positive—on CHC's standard care SBIRT screening administered during medical visits by a medical assistant. Each weekday, the CHC BI ran an automated query on CHC's electronic data warehouse to identify patients who meet the study inclusion criteria, listed above, for the Universal Recruitment Approach AND who completed the DAST and AUDIT-C on the previous weekday and scored in the moderate- or high-risk range on either measure. The Project Manager took the list, removed any patients who declined participation in response to the original email and called the remaining at-risk patients to introduce the study and ask permission to send an email invitation with a link to the study website. The Project Manager confirmed the email address of the participants who agreed to be contacted. Each day the Project Manager sent Pro-Change a list of patients who agreed to be invited, and Pro-Change sent out the email invitations.

Patients who complete the ASSIST via Connect2BWell fell into one of six groups

- Group 1 – Screened negative for Substance Use Disorder (SUD) on the ASSIST. A report of the ASSIST results was assigned to their Primary Care Provider (PCP) through the Electronic Medical Record (EMR).
- Group 2 – Screened positive for SUD on the ASSIST but not enrolled in the study due to screening out, not completing baseline, or not consenting. A report of the patient's ASSIST results was provided to the patient's PCP through the EMR. The patient's PCP's nurse contacted the patient to deliver a brief intervention and referred them to behavioral health or specialty treatment if indicated.
- Group 3 – Screened positive for SUD on the ASSIST and assigned to the Comparison Condition. As in Group 2, a report of the patient's ASSIST results was provided to their PCP in the EMR. The PCP's nurse contacted the patient to deliver a brief intervention and referral to behavioral health or specialty treatment if indicated. These patients received an initial email notification—with up to 9 email and text reminders, 5 calls, a mailed flyer, and calls to collateral contacts—to complete additional study assessments.
- Group 4 – Screened positive for SUD on the ASSIST and assigned to the *Connect2BWell* Condition. The patient was transitioned seamlessly from the online *Connect2BWell* screening questions and consent form to the intervention portion of the session. After the session, a report of the patient's ASSIST results was assigned to the study's Nurse Care Manager (NCM) in the EMR. The study's NCM contacted the patient to deliver a brief intervention guided by the *Connect2BWell* Clinical Dashboard and made a referral to behavioral health or specialty treatment if indicated. The patient received additional *Connect2BWell* online sessions at 1 and 3 months follow-up. Each online session was followed by a Clinical Dashboard-guided one-on-one session with the study's NCM. The patient also received 6 months' of stage-matched text messages and access to a patient portal with tools and activities to support and facilitate change. These patients received an initial email notification and the same schedule of reminders as the Comparison group to complete additional study assessments.
- Group 5 – Recruited via the Targeted Approach and assigned to the Comparison Condition. These patients had already completed CHC's standard SBIRT screening and brief intervention.

- Group 6 – Recruited via the Targeted Approach and assigned to the *Connect2BWell* Condition. While these patients had already completed CHC's standard SBIRT screening and brief intervention, their ASSIST results were assigned to the study NCM in the EMR and they received the study intervention.
- Groups 3 and 5 comprise the Comparison group and groups 4 and 6 comprise the *Connect2BWell* treatment group. Both groups are prompted to complete follow-up online assessments 3, 6, and 9 months. Non-respondents received up to 9 email and text reminders, 5 calls, a mailed flyer, and calls to collateral contacts.

Analysis Plan

The analysis will use mixed effects models that account for repeated measures within participants through a random intercept for participants. Fixed effects will include group (treatment vs control), time, and time-by-group interaction. Analyses will be conducted for the primary outcome measure of change from baseline in days of use of the most problematic drug in the previous 30 days at 9 Months. Secondary outcome measures include the change from baseline in ASSIST score for most problematic drug at 9 months and the change from baseline in ASSIST score for total substance involvement at 9 months as well as the change from baseline in depression at 9 months.

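### The primary model omits baseline drug class and severity, two factors that shape what the program delivers, and the plan cannot show whether the effect is consistent across them

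*Combined protocol and SAP*

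**What the plan says.** The opening program description lists four dimensions on which the program is tailored. The first two are "Their most problematic drug (i.e., the drug with the highest risk score") and "Their risk severity (i.e., moderate or high) for their most problematic drug". The other two concern readiness: "Their readiness to quit their most problematic drug or, for prescription drugs, to use as prescribed" and, for part of the sample only, "Their readiness to seek treatment if their risk severity score is in the “high” range".

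The list of patient groups under Targeted Approach describes patients who completed the ASSIST through the program. The four enrolled groups (3 to 6) belong to that list, so drug and severity scores exist at baseline in both arms.

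The Analysis Plan takes as primary outcome the 9-month change in days of use, over the past 30 days, of the patient's most problematic drug. The mixed models "account for repeated measures within participants through a random intercept for participants". The fixed part is given in one sentence: "Fixed effects will include group (treatment vs control), time, and time-by-group interaction". No covariate, stratification factor, subgroup or interaction with drug or severity appears anywhere in the document.

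**The concern.** Drug and severity are not arbitrary subgroups here, because they help decide what a patient in the treatment arm receives. They may well also predict how days of use change over nine months. The outcome itself refers to alcohol in one patient and another drug in the next. For prescription drugs the stated goal is use as prescribed, and the plan does not say whether a day of prescribed use counts as a day of use.

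Two things are at stake. First, baseline information that is already collected is not used to sharpen the primary estimate. Second, the planned analysis returns one arm effect and offers no view of whether that effect is similar for alcohol and other drugs, or for moderate and high risk. Readers of a tailored program will ask that question.

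**Working it through.** **Inputs.** The documents give the model terms, the outcome and the tailoring dimensions. They give no sample size, SD, effect size, alpha, power, allocation ratio, or mix of drugs or severities. There is therefore no planned figure to reproduce, and every number below is an assumption: 200 per arm, SD of change 10 days, 60% alcohol and 40% other drugs, a 3-day difference, two-sided alpha 0.05.

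**1. What the pooled contrast estimates.** It is approximately the share-weighted mean of the stratum effects.
- Equal benefits of 3 days in moderate and high risk: pooled 3.0 days for any mix.
- Benefits of 4 days (moderate) and 1 day (high): pooled 3.4, 3.1 or 2.5 days when 20%, 30% or 50% are high risk; for example 0.8 × 4 + 0.2 × 1 = 3.4.
- Benefits of 3 days (alcohol) and 0 (other): 0.6 × 3 + 0.4 × 0 = 1.8 days.

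The average fits everyone when effects are equal. It departs clearly from both strata only when effects differ a lot and neither stratum dominates.

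**2. Precision gained by adjustment.** The SE ratio is √(1 − R²), with R² the share of residual variance explained.
- R² = 0.05: √0.95 = 0.975, an SE about 2.5% smaller.
- R² = 0.10: √0.90 = 0.949, an SE about 5% smaller.

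The participant random intercept already absorbs stable differences in level. The gain must come from differences in change by drug or severity, which is why each factor needs its interaction with time.

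**3. Precision of contrasts by drug class.** SE = SD × √(2/n per arm).
- Pooled: 10 × √(2/200) = 1.00 day.
- Alcohol (120 per arm): 10 × √(2/120) = 1.29; 95% CI half-width 1.96 × 1.29 = 2.5 days.
- Other drugs (80 per arm): 10 × √(2/80) = 1.58; half-width 3.1 days.
- Difference between the two effects: √(1.29² + 1.58²) = 2.04; half-width 4.0 days.
- Power to detect a 3-day difference in effect: Φ(3/2.04 − 1.96) = Φ(−0.49) ≈ 31%.

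Range, still with 200 per arm:

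| SD | Split | SE of difference | Power for 3 days |
|---|---|---|---|
| 10 | 50/50 | 10 × √(2/100 + 2/100) = 2.00 | 32% |
| 10 | 80/20 | 10 × √(2/160 + 2/40) = 2.50 | 22% |
| 8 | 60/40 | 0.8 × 2.04 = 1.63 | 45% |
| 12 | 60/40 | 1.2 × 2.04 = 2.45 | 23% |

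**4. The same question for severity.** At 80% power, SD 10 and 1:1 allocation, the pooled comparison needs 350 in total for 3 days. For a moderate-versus-high difference in effect of the same size, total N = 4 × SD² × (1/p + 1/(1 − p)) × (1.960 + 0.842)² / 3², with p the high-risk share.
- p = 0.5: 1,396 (about 4.0 times 350).
- p = 0.3: 1,662 (about 4.75 times).
- p = 0.2: 2,181 (about 6.2 times).

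At 350 in total, power for that interaction is 29%, 25% and 20% respectively.

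**The case against.** The strongest reply is that tailoring is part of the intervention. The trial compares offering one tailored program with the comparison condition, and the average effect over the enrolled mix is a legitimate and useful quantity. Different content does not imply different effects; tailoring may even be meant to equalise benefit. **This stands.** A reader might infer that the pooled result describes none of the patients, or that a benefit in one drug group will be credited to the rest. The documents support neither reading. They contain no evidence of heterogeneity, the plan makes no claim by drug or severity, and with equal effects the pooled figure fits every stratum.

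A second reply is that subgroup contrasts would usually leave the question open. On the assumed inputs this is also right: a 4-day half-width on the difference settles little. It argues for labelling the contrasts exploratory. It does not argue for leaving them unplanned, since a specified estimate with its interval is better than a subgroup chosen after the results are seen.

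A third reply is that the random intercept already does most of the work of adjustment. This stands for stable levels of use but not for change that differs by drug or severity.

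A fourth is that readiness is a tailoring dimension too, so choosing drug and severity is selective. This has some force. However, the documents do not say that readiness is measured before assignment in both arms, whereas drug and severity scores come from a screen that both arms complete. Finally, days out of 30 is a common unit. That is so; what a day of use means for different drugs is a matter of interpretation, not a modelling error.

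**Conclusion.** The point holds as a modest gap in precision and reporting. The model omits two baseline factors that are already collected, help define the treatment delivered and are likely to predict change. The plan has no analysis that could show whether the effect is consistent across them.

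The primary contrast is not invalidated. Leaving the factors out does not by itself bias it if allocation was random; the documents say that patients were assigned to condition without stating how. Nor does the omission show that the program works differently by drug or severity.

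The precision gain is about 2.5 to 5% of the SE, on an assumed 5 to 10% of residual variance explained. On the assumed 200 per arm, SD 10 and 60/40 split, the drug-class interaction has an SE of about 2.0 days and about 31% power for 3 days, so it can inform but not decide. The documents supply none of these inputs.

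**What to change.** In the Analysis Plan:

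1. Add baseline drug class (alcohol versus other, fixed in advance) and baseline severity (moderate versus high) to the primary model, each with its interaction with time.
2. Keep the pooled month-9 arm contrast as primary, state that it averages over the enrolled mix of drugs and severities, and report that mix by arm.
3. Specify month-9 arm contrasts by drug class and by severity, each with its interaction estimate and 95% CI, labelled exploratory.
4. If outcomes by arm have already been examined, label the subgroup contrasts post hoc, and show the adjusted model beside the planned one as a sensitivity analysis.
5. State whether prescribed use counts as a day of use, so that the outcome can be read for prescription drugs.

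The cost is SAP wording and two more model runs, with no new data. The adjusted model carries a few extra parameters: with baseline and three follow-ups as categorical times, 2 × (1 + 3) = 8. The subgroup estimates will be imprecise and should be presented as such.

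### The primary model pools two recruitment routes with different background care and has no route term; adding one is cheap, though no bias is shown.

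*Combined protocol and SAP*

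**What the plan says.** The last bullet of the group list, just before the Analysis Plan, forms the two arms: "Groups 3 and 5 comprise the Comparison group and groups 4 and 6 comprise the" Connect2BWell treatment group. The Analysis Plan then specifies a mixed model with a participant random intercept: "Fixed effects will include group (treatment vs control), time, and time-by-group interaction". No covariate, stratum, interaction, subgroup or sensitivity analysis by recruitment route is named.

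The group descriptions give different background care:

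- **Group 3 (comparison):** after the ASSIST report reaches the primary care provider, that provider's "nurse contacted the patient to deliver a brief intervention and referral to behavioral health or specialty treatment if indicated".
- **Group 4 (Connect2BWell):** the report goes to the study's Nurse Care Manager (NCM) instead. The "NCM contacted the patient to deliver a brief intervention guided by the" program's dashboard. No nurse-delivered standard session is described.
- **Group 5 (comparison):** "Recruited via the Targeted Approach and assigned to the Comparison Condition. These patients had already completed" the clinic's standard screening and brief intervention.
- **Group 6 (Connect2BWell):** these patients had likewise completed "standard SBIRT screening and brief intervention, their ASSIST results were assigned to the study NCM in the EMR and they received the study intervention".

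Entry differs too. Under the Targeted Approach, patients meet the Universal criteria and are also people "who completed the DAST and AUDIT-C on the previous weekday and scored in the moderate- or high-risk range on either measure".

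**The concern.** Read literally, the two routes carry two comparisons. Group 4 versus Group 3 looks like the program in place of a standard brief intervention. Group 6 versus Group 5 looks like the program on top of one already given. A single group-by-time contrast averages them, with weights set by how many patients came through each route.

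Two things follow. First, if the route effects differ, the pooled figure describes the recruited mix, and a service with another mix could not carry it over directly; nothing in the plan would show what the average contains. Second, route is a baseline characteristic that may predict the outcome. The group descriptions say only that patients were assigned, and this document describes no stratification by route. If the arms differ in their share of Targeted patients, the planned model does not correct for it.

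**Working it through.** The plan states no effect, SD, sample size, allocation ratio or route mix, so there is no figure of its own to reproduce. Every numerical input below is an assumption.

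**1. What the pooled contrast averages.** Let P be the effect of the program alone, B the effect of one standard brief intervention, and w the Targeted share, with equal allocation within route.

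*If the two effects add:* Group 4 − Group 3 = P − B, and Group 6 − Group 5 = (P + B) − B = P. The pooled contrast is (1 − w)(P − B) + wP = P − (1 − w)B. With P = −3 days:

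| B (days) | w = 20% | w = 40% | w = 60% |
|---|---|---|---|
| −0.5 | −2.6 | −2.7 | −2.8 |
| −1 | −2.2 | −2.4 | −2.6 |

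Moving w from 20% to 60% changes the result by 0.4 × |B|, that is 0.2 or 0.4 days.

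*If the standard session adds nothing for someone who also gets the program:* Group 6 has effect P and Group 5 has effect B, so both contrasts equal P − B. With B = −1 that is −2.0 days at every mix.

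These are two scenarios, not limits. Synergy would widen the gap between routes and interference could reverse it.

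**2. Chance imbalance.** Assume N = 400 allocated 1:1 independently of route, SD of change 10 days, w = 0.4.

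- Pooled SE = √(4 × 10² / 400) = 1.00 day.
- SD of the between-arm difference in Targeted share = √(4 × 0.4 × 0.6 / 400) = 0.049, or 4.9 percentage points.
- If the routes differ by d days in mean change, the typical shift is 0.049 × d: 0.10 days for d = 2 and 0.20 days for d = 4.

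These shifts average to zero over repeated allocations, so this is noise and not bias. A simulation of change scores under these assumptions (6,000 runs, true effect −3) gave unadjusted means within about 0.03 days of −3.

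**3. Precision gained by adjusting.** Share of variance removed = w(1 − w)d² / SD².

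- d = 2: 0.24 × 4 / 100 = 0.96%; SE = √(1 − 0.0096) = 0.995.
- d = 4: 0.24 × 16 / 100 = 3.84%; SE = √(1 − 0.0384) = 0.981.

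The SE falls by about 0.5% to 2%. What matters is how the routes differ in change, so if baseline is one of the repeated measures the approach-by-time term does the work; a main effect alone would absorb only a constant difference in level.

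**4. What route-specific estimates could show.** With the pooled SE at 1.00, the route SEs are about 1/√(1 − w) and 1/√w, and the SE of their difference is 1/√(w(1 − w)).

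| w | 95% half-width, 4 vs 3 | 95% half-width, 6 vs 5 | SE of difference | Power, 1-day difference | Power, 3-day difference |
|---|---|---|---|---|---|
| 20% | 2.2 | 4.4 | 2.50 | 6.9% | 22.4% |
| 40% | 2.5 | 3.1 | 2.04 | 7.8% | 31.2% |

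Power is two-sided at 5%. Even at w = 50% (SE 2.00) it is only 7.9% and 32.3%. These estimates describe; they cannot test.

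**The case against.** The strongest reply is that nothing is wrong with the pooled contrast. As described, both comparison groups have standard SBIRT, one through the nurse and one at the visit, so the pooled comparison asks a coherent question: program versus standard care, over the two routes used. Within one trial the mix is fixed. The illustrated movement of at most 0.4 days is small beside an SE of 1.0, and every input is assumed. All of this stands, and it is why the pooled contrast should remain primary.

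It is also fair to say that the route-specific contrasts would not settle replacement versus addition. Targeted patients had to screen positive on a further instrument and had not completed the online ASSIST before their visit, so a gap between the two contrasts could reflect who was recruited. The replacement reading is itself partly inferred: Groups 3 and 4 are not labelled Universal, and the text does not say whether Group 4 also had standard SBIRT at a visit. Nor is telephone contact a clean marker of the Targeted route, since Universal recruitment also included email invitations "with a telephone call on day 4 from the CHC Project Manager to a random sample of non-respondents".

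The reply does not remove the case for a route term. The variable defines the groups, is known for everyone, and costs almost nothing to include. The small gain is matched by a small price.

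**Conclusion.** The point holds as a low-cost improvement to consider, not as an error. The plan pools two routes whose described background care differs and has no term or display for route. Under the stated assumptions, adjustment protects against a typical chance shift of 0.10 to 0.20 days and cuts the SE by about 0.5% to 2%.

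A reader might infer three stronger things that the documents do not support.

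- **That pooling biases the treatment effect.** If allocation was independent of route, the pooled contrast is an unbiased average.
- **That the arms are unbalanced by route.** The text reports no imbalance; it only leaves balance unconfirmed. Were allocation to depend on route, the unadjusted model could be confounded, but that is conditional.
- **That splitting by route would isolate the effect of a prior brief intervention.** Selection by route and low precision prevent it.

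**What to change.** 1. Add recruitment approach (Universal or Targeted) and approach-by-time as fixed effects in the primary and secondary models. Keep the pooled group-by-time contrast at 9 months as the primary result, and describe it as an average over the observed route mix.
2. Report the number of participants by arm and route.
3. From one approach-by-group-by-time model, give the 9-month contrasts for Group 4 versus 3 and Group 6 versus 5 with 95% confidence intervals, as descriptive only. State beside them that they are imprecise, are confounded with selection by route, cannot separate replacement from addition, and support no claim of equal or different effects.

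The cost is a few fixed-effect degrees of freedom and one table, with no new data collection.

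### A participant random intercept is the only stated handling of repeated measures, so the month-9 standard error may be wrong, and too small if within-person correlation falls with time

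*Combined protocol and SAP*

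**What the plan says.** The Analysis Plan is one paragraph at the end of the combined protocol and SAP. It calls for "mixed effects models that account for repeated measures within participants through a random intercept for participants". On the mean structure it says: "Fixed effects will include group (treatment vs control), time, and time-by-group interaction". The primary outcome is "change from baseline in days of use of the most problematic drug in the previous 30 days at 9 Months", and the secondary outcomes (two ASSIST scores and depression) are also changes from baseline at month 9.

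The schedule comes just before, at the end of the group descriptions: "Both groups are prompted to complete follow-up online assessments 3, 6, and 9 months". With baseline, that makes four occasions. Non-response is expected: "Non-respondents received up to 9 email and text reminders, 5 calls, a mailed flyer, and calls to collateral contacts".

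Four things are not stated anywhere:
- a residual covariance structure, random slope or robust standard error;
- whether time is categorical or continuous;
- whether the response is the raw score at months 0, 3, 6 and 9 or the change score at months 3, 6 and 9;
- any correlation or SD that would support constant variance and constant correlation.

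**The concern.** With independent residuals, a random intercept gives every visit the same variance and every pair of visits the same correlation, whether they are 3 or 9 months apart. The model then estimates one residual variance from all visits and uses it for the baseline-to-month-9 contrast. Measurements on one person often become less alike as they move apart in time. If that happens here, the pooled correlation is higher than the 9-month correlation that governs the primary contrast, and the reported standard error is usually too small.

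At stake are the p-value and confidence interval for the primary outcome, and for the secondary outcomes if they are fitted the same way. Both would be valid only under an assumption that the plan neither justifies nor checks. With missing data, the assumed covariance also decides how months 3 and 6 stand in for an absent month-9 value.

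**Working it through.** The plan gives no sample size, power, alpha, SD or correlation, so there is no figure of its own to reproduce. The check compares the variance that the model would report for the month-9 group difference with its true variance.

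**Inputs.** From the documents: visits at months 0, 3, 6 and 9; random intercept only; contrast of baseline with month 9. Assumed: two-sided 5%, a linear model with normal data, the same covariance in both arms, a separate mean for each group at each visit, complete data, and the correlations and SDs below.

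**Formulas.** Let S be the covariance matrix of the four visits. Factors for group size cancel.
- True variance, both readings: S00 + S99 − 2·S09.
- Raw scores at four visits: the model reports 2 × (mean diagonal of S − mean off-diagonal of S).
- Change scores at three visits: the model reports the mean over j = 3, 6, 9 of Var(Yj − Y0).
- SE ratio = √(model/true). Type I error = 2 × (1 − Φ(1.96 × ratio)).

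**Worked case: lag correlations 0.60/0.55/0.50, SDs all 1.** Of the six visit pairs, three are at one step, two at two steps and one at three.
- Raw: mean off-diagonal = (3×0.60 + 2×0.55 + 0.50)/6 = 0.567. Model variance = 2 × (1 − 0.567) = 0.867; true = 2 × (1 − 0.50) = 1.000. Ratio √0.867 = 0.931, error 6.8%.
- Change: the three change variances are 0.80, 0.90 and 1.00, mean 0.90; true 1.00. Ratio √0.90 = 0.949, error 6.3%.

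**All cases** (type I error, raw / change):

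| Correlation pattern | SDs equal | SDs 0.7/1/1/0.9 | SDs 0.7/0.8/0.9/1 |
|---|---|---|---|
| 0.60/0.55/0.50 by lag | 6.8% / 6.3% | 4.1% / 4.8% | 7.4% / 8.3% |
| 0.65/0.55/0.45 by lag | 8.8% / 7.6% | 5.6% / 5.9% | 9.3% / 9.5% |
| First-order decay, 0.7 per visit | 11.3% / 9.1% | 7.6% / 7.3% | 11.6% / 10.8% |
| Baseline to follow-up 0.4, between follow-ups 0.65 | 8.1% / 5.0% | 5.3% / 3.9% | 9.1% / 6.9% |
| Flat 0.5 | 5.0% / 5.0% | 2.8% / 3.8% | 5.6% / 7.0% |

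The equal-SD ratios for the first four rows are 0.931, 0.870, 0.809 and 0.890 (raw) and 0.949, 0.905, 0.863 and 1.000 (change).

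**A case that reverses: flat 0.5, SDs 0.7/1/1/0.9, raw scores.** The mean variance is (0.49 + 1 + 1 + 0.81)/4 = 0.825. The covariances are 0.35, 0.35, 0.315, 0.50, 0.45 and 0.45, mean 0.4025. Model variance = 2 × (0.825 − 0.4025) = 0.845; true = 0.49 + 0.81 − 2×0.315 = 0.67. Ratio 1.123, error 2.8%: the standard error is too large.

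**Linear time.** If time is continuous and baseline is a response, first-order decay at 0.7 with equal SDs gives a ratio of 0.758 and an error of 13.7%; 0.60/0.55/0.50 gives 0.913 and 7.4%.

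**Simulation** (random-intercept model by REML, raw scores, n = 200, 2,500 runs, Monte Carlo error about 0.5 points). Complete data, equal SDs, first three patterns: 6.5%, 8.7%, 11.8%; flat 0.55: 5.2%. With random dropout of 10/20/30% by months 3/6/9: 6.2%, 7.6%, 9.9%; flat 0.55: 4.6%.

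**Weighting under dropout** (n = 400,000, no true effect). If dropout depends on the previous score in opposite directions in the two arms, with about 38% missing at month 9, the bias is 0.02, 0.04 and 0.07 SD for the first three patterns. With the same dropout rule in both arms it is about 0.01 SD or less.

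**The case against.** The strongest reply is that the plan is under-specified rather than wrong. A random intercept can be combined with a structured residual or robust standard errors, and the final code may do so. Under compound symmetry the planned model is correct. Every figure above rests on assumed inputs: the results fall on both sides of 5%, several are trivial, and the largest need strong decay (a 9-month correlation of 0.34) that nothing in the documents supports. Days of use out of 30 is a bounded count, and in a count or binomial mixed model the variance follows the mean, so neither the equal-variance statement nor these formulas would apply.

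Much of this stands as a limit on size and direction. It does not remove the point. The plan names one device for repeated measures and adds nothing to it; settling the covariance after the data are seen is what an analysis plan should prevent. An outcome expressed as a change in days points to a linear model. The dropout weighting effect is small, and its larger values need a contrived pattern, so it adds little weight. Robust standard errors alone would repair the standard error; unstructured covariance is one defensible choice, preferred because it also deals with the weighting.

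**Conclusion.** The concern holds, with moderate confidence, and should be fixed. Followed as written, with independent residuals and model-based standard errors, the plan gives a month-9 standard error that is right only under equal variance and equal correlation, or where departures happen to cancel. Across the categorical-time cases in the table the actual error at a nominal 5% runs from 2.8% to 11.6%. That is the span of the chosen cases, not a bound, and the linear-time reading goes higher. With equal SDs and correlation falling at each lag, the test is too liberal under both readings. Unequal SDs can cancel or reverse this. Since the documents give no correlations or SDs, neither the size nor the direction in this trial is known. The conclusion assumes a linear model.

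**What to change.** In the Analysis Plan, state whether the response is the raw score or the change score. Fit time as categorical with an unstructured within-participant covariance over the modelled visits, using REML with Kenward-Roger or Satterthwaite degrees of freedom, for the primary and secondary outcomes. With complete data the month-9 test is then the two-sample test of change, which holds 5% in every case tabulated above (normal data, same covariance in both arms).

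Name the fallback in advance: if the model does not converge, keep the random intercept and use participant-clustered sandwich standard errors. That corrects the standard error but not the weighting of months 3 and 6 under dropout.

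The cost is one or two sentences and no new data. The covariance has 10 parameters for four raw scores (6 for three change scores) instead of 2, and the interval may be wider.
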